### Study Measures

**Table 2. Timetable of Study Measures During Feasibility Trial**

Evaluation/Study Week	Baseline	Weeks 2-3	Week 4
Screening and Qualification	X		
Medical Chart History Review	X		
Dependent Variable Measures			
Phantom Limb Pain Questionnaire (PLPQ)	X	X	X
Trinity Amputation and Prosthetic Experience Scale (TAPES)	X	X	X
Pain Interference (Brief Pain Inventory, SF-12)	X	X	X
Pain Intensity (Numerical Pain Rating Scale)	X	X	X
Mood (BDI)	X	X	X
Treatment Credibility/Feasibility & side effects	X	X	X
Treatment Satisfaction		X	X
Immersiveness of mirror therapy experience		X	X

#### *Satisfaction, Feasibility, and Validity Measures*

**1. Client Satisfaction Questionnaire-Revised (CSQ):** measures satisfaction with health care treatment on a four-point Likert scale. **2. Credibility-Expectancy:** Likert-style ratings (0-6) will monitor participant expectations, credibility, and belief in the relevance and usefulness of treatment. **3. Igroup Presence Questionnaire (IPQ):** a measure used to assess immersiveness of VR-type artificial environments that contains subscales assessing three components of presence, spatial presence, involvement, and realness. **4. Side effects:** participants will complete a check list of side effects used by our VR researchers in the prior development testing (e.g., dizziness, headaches, nausea, history of motion sickness).

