#### **VR Mirror Therapy Condition**

Using a VR headset, motion sensors, and VR software, we will create a customized VR treatment for

each participant that engages them in movements and exercises involving their missing limb in a game-like environment. For example, participants may use the headset to engage in activities such as driving a race car around a course requiring both arms, ski down simulated slopes (see illustration), or manipulate objects. We will use a validated “presence” questionnaire to assess realism and level of immersiveness by participants. Preliminary studies of VR among patients with PLP suggest they interpret VR simulations as realistic representations of their body, including physiological responses when engaging the avatar in motion. Compared to standard mirror therapy, the VR adaption to mirror therapy has unique advantages, such as the ability for the avatar to engage in a much broader range of activities and comparatively diminished fatigue compared to usual mirror therapy exercises. The latter advantage may allow VR participants to obtain longer and more frequent mirror therapy treatments that could enhance the intervention. We can also modify the VR environment specifications for participants reporting a history of motion sickness – for example, by decreasing the degree of sensitivity to head movements – to minimize side effects and improve usability.

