Feasibility outcomes – including satisfaction, adherence, side effects, and mood and PLP changes – will be compared pre-to-post treatment separately for the VR and mirror therapy protocols and between the two treatments. Participants will utilize each treatment for one month. This treatment duration is consistent with periods allowing for pain symptom reductions in previous VR studies and for PLP changes in mirror therapy participants. During this phase, participants will complete in person baseline and weekly visits for four weeks with either the VR technical staff (VR) or study coordinator (mirror therapy) in addition to their daily homework exercise recommendations. Following IMMPACT (Initiative on Methods, Measurement and Pain Assessment in Clinical Trials) guidelines, the baseline and post-treatment visits will include measures of PLP (Phantom Limb Pain Questionnaire (PLPQ), adjustment to amputation and prosthesis (Trinity Amputation

and Prosthetic Experience Scale (TAPES), mood (Beck Depression Inventory), and life quality (Medical Outcomes Study (SF-12). The study coordinator will administer the assessment measures with both treatment groups. Team statistician, [name], will receive outcome data blinded to treatment assignment.

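### The side-effect checklist comes from VR testing and is not shown to capture mirror-therapy burdens such as exercise fatigue, so the planned between-arm comparison may be biased against VR

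*Combined protocol and SAP*

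**What the plan says.** All references are to the combined protocol and SAP.

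- **Comparison planned.** The section on the Year 2 feasibility trial phase defines the feasibility outcomes as "including satisfaction, adherence, side effects, and mood and PLP changes". It says that they "will be compared pre-to-post treatment separately for the VR and mirror therapy protocols and between the two treatments".
- **Same measures in both arms.** The same section states: "The study coordinator will administer the assessment measures with both treatment groups". Table 2 (Study Measures) schedules side effects at baseline, weeks 2-3 and week 4, with no distinction by arm.
- **Instrument.** Under Satisfaction, Feasibility, and Validity Measures, participants are to complete "a check list of side effects used by our VR researchers in the prior development testing (e.g., dizziness, headaches, nausea, history of motion sickness".
- **Burden attributed to mirror therapy.** The VR Mirror Therapy Condition section credits VR with "comparatively diminished fatigue compared to usual mirror therapy exercises". It adds that this may permit longer and more frequent treatment.

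**The concern.** A fair comparison of side effects needs an instrument that can register what each treatment is likely to cause. Here the list comes from testing one of the two treatments, and every treatment-emergent example is a symptom one would look for in a headset user. The one burden that the plan assigns more to mirror exercises, fatigue, is not among the examples. If mirror complaints go unrecorded while VR complaints are recorded, VR looks worse than it is. That is a systematic error, and it would carry into the planning of the larger trial. The expected fatigue advantage of VR would also have no direct measurement.

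The history of motion sickness is a separate defect. It describes the participant before treatment, and the VR Mirror Therapy Condition section uses it to adjust the VR environment. Treatment cannot cause it.

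**Working it through.** The plan gives no side-effect rate and no figure to reproduce. The check is mainly a reading of the passages side by side, followed by an illustration with assumed rates.

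**1. Could another described measure capture treatment fatigue or other mirror-specific complaints?**

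- *Real-time VR questions* (Real-Time VR Embedded Pain Assessment): these can cover phantom limb pain (PLP), mood, immersiveness or side effects. No item content is given.
- *Mirror-arm home log* (Standard Mirror Therapy Condition): it asks the same questions as VR participants answer. It is a second channel, but it carries over the VR question set.
- *SF-12* (Pain, Mood, and Functional Measures): it includes vitality, as general health status and not as an effect of treatment.
- *Open feedback*: this is described for the Year 1 usability phase. No open side-effect question is described for Year 2.
- *PLPQ*: it scores PLP and stump pain and is scheduled in both arms at baseline, weeks 2-3 and week 4. Worsening pain is therefore measured, though no passage links it to side-effect reporting.

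What remains uncovered, on the text as written, is treatment fatigue and any complaint that the checklist does not name.

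**2. What would incomplete capture do?**

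Assume the same true rate p in both arms, full capture in the VR arm, and a captured share c in the mirror arm. With n = 10 per arm (section C):

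- recorded mirror rate q = p × c
- false VR excess = p − q
- 95% half-width = 1.96 × √[p(1−p)/10 + q(1−q)/10]

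For p = 0.30 and c = 0.50: q = 0.15 and the excess is 0.30 − 0.15 = 0.15. The half-width is 1.96 × √(0.021 + 0.01275) = 0.36.

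| Assumed true rate p | c = 1 | c = 0.75 | c = 0.50 | c = 0 |
|---|---|---|---|---|
| 20% | 0 (±35) | 5 (±33) | 10 (±31) | 20 (±25) |
| 30% | 0 (±40) | 7.5 (±38) | 15 (±36) | 30 (±28) |
| 50% | 0 (±44) | 12.5 (±43) | 25 (±41) | 50 (±31) |

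Entries are the false VR excess in percentage points, with the half-width in brackets. Both p and c are assumptions. In this grid the false excess is larger than the half-width only when nothing is captured in the mirror arm and p is 30% or 50%.

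**3. What would motion-sickness history do?**

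If it were counted as a side effect, each person with that history and no other complaint would add 1/10 = 10 percentage points to their arm's figure at a visit. Because it is fixed, it would be ticked at baseline too, and it cancels from a pre-to-post change in the number of items ticked. It can distort a raw proportion at one visit. No passage says how the checklist will be scored.

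**The case against.** The strongest reply is that the four items are introduced as examples. The full checklist may already contain fatigue, and the text says that the VR researchers used it, not that it was designed for VR alone. This stands. A reader might infer that the checklist has no fatigue item and that the comparison is therefore tilted; the documents show neither. A reader might also take an extreme outcome, such as 30% against 0%, as the expected result. That figure rests wholly on assumed rates and zero capture in the mirror arm.

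Second, pain made worse by the exercises is not a gap in measurement, since the PLPQ scores phantom and stump pain in both arms. This also stands, and only the reporting alongside side effects is open.

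Third, the consequence is limited. Table 1 lists side effects among the Year 1 outcomes but not in the Year 2 row, and the feasibility measures listed in section C omit them. Section C also says that the trial is not powered for between-group differences. This lowers the importance of the point but does not remove it: the Year 2 section still names the comparison, and imprecision does not excuse a systematic error that better wording of the form could prevent.

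Fourth, fatigue matters to the plan partly through longer practice, and practice time is tracked by the headset and recorded in the mirror log. That gives indirect evidence. It does not record fatigue as a complaint.

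**Conclusion.** The point holds as a minor one. A between-arm comparison of side effects is planned, its only described instrument comes from VR development testing, and nothing in the plan shows that it captures burdens of mirror therapy such as the fatigue the plan itself mentions. No open question is described for Year 2 that would catch what the list leaves out. The comparison may therefore be biased against VR. That direction assumes that VR complaints are captured more completely than mirror complaints. The size cannot be estimated from the documents: it is zero if the full list covers both treatments equally, and it otherwise depends on checklist content and complaint rates that are not given.

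Listing motion-sickness history among side effects is an error of classification that can be seen in the text whatever the rest of the list contains. Its effect on pre-to-post change is nil if the history is recorded consistently.

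**What to change.** Under Satisfaction, Feasibility, and Validity Measures:

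1. State the full checklist, and confirm or add, for both arms, an item on fatigue from the exercises or treatment and a free-text item for other complaints.
2. Collect motion-sickness history once, at baseline, and exclude it from all side-effect counts.
3. Report increases from baseline in the PLPQ phantom pain and stump pain items by arm, in the same table as the side effects. These data are already being collected.

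The cost is about two checklist lines and a table row or two. The downside is that the revised list is no longer identical to the one used in earlier VR testing, so only the original items can be compared with those data.

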#### *Pain, Mood, and Functional Measures*

**1. Phantom Limb Pain Weekly Questionnaire (PLPQ).** The PLPQ assesses the severity of PLP, stump pain and phantom limb sensation. Severity is assessed on a standard 11-point Likert scale pain measure, as recommended by the IMMPACT review group. **2. Trinity Amputation and Prosthetic Experience Scale (TAPES):** includes 27 items measuring activity, social functioning, and pain associated with the amputation, including PLP. **3. Short Form – 12 (SF-12):** measures physical functioning, general health, vitality, social functioning, and mental health. **4. Numeric Rating Scale (NRS):** current pain intensity (0=No Pain, 10= Pain as bad as you can imagine). **5. Brief Pain Inventory (BPI):** interference subscale rates pain interference in everyday contexts (e.g., activity, sleep, relationships) on a Likert type scale. **6. Beck Depression Inventory (BDI):** The BDI is a standard index of depressed mood.

#### **Summary of study strengths and innovation contributions**

1. Adapts mirror therapy for PLP to a patient centered VR treatment easily used by patients at home.
2. Boasts a team of experienced chronic pain researchers with successful prior experience carrying out an R&D-funded PLP trial in combination with VR development expertise.
3. Brings affordable, state of the art VR technology to the care of Veterans with PLP including features to measure real-time effects of VR treatment on PLP.
4. Includes a feasibility trial assessing the treatment in comparison to standard mirror therapy.
5. Explicitly uses the feasibility trial phase as a crucial step in collecting effect size, adherence, and satisfaction data for a larger scale comparative effectiveness trial evaluating benefits of the VR.

#### **Long term study objectives**

The long terms aims are to evaluate the efficacy of the VR treatments in a larger scale randomized controlled trial, to explore biological mechanisms explaining PLP reductions – such as changes in somatosensory cortex activity viewable pre- and post-VR treatment through fMRI – and to expand the VR treatment to be usable by double limb as well as single limb amputees.

#### **Conflict of interest statement**

The study proposal is designed to minimize potential conflicts of interests. The VA investigator team will conduct the clinical trial, maintain the study database, and perform all statistical analyses independent of the VR developers. The VA investigators have no financial relationships with the VR industry.

### C. Data Management and Statistical Analyses

Data management and analysis will be conducted using SPSS and R statistical software and carried out by co-investigator and study senior statistician, [name]. Qualitative data will be coded and categorized for analysis. The primary aims of our data analytic strategy in year 1 will be directed toward the collection of data that will inform modification of the VR treatment. In year two it will be directed toward examining the feasibility of the VR treatment. We would like to emphasize that although we will estimate effect sizes to assist in future power calculations, this is not our major focus. Recent work by Kraemer highlights important limitations of this aim due to the large standard error surrounding the pilot study effect size. Our goal is to collect important data regarding the development of VR treatment and optimized recruitment strategies. Information derived from our research will lead to better-designed full-scale studies and informs decisions regarding whether it is worthwhile to commit additional resources to future VR treatment development.

For quantitative data, descriptive statistics will be used to summarize the variables as well as detect outliers and data entry errors. When applicable, normality of the distribution will be examined for outcome variables. Other preliminary analyses will include evaluation of patterns of missing data, dropout rates, distributional properties of variables, and correlations among measures. Although there are important limitations associated with the analysis of our year 2 data, we do propose to conduct limited statistical analyses. First, we will calculate an estimated effect size for our primary outcome in the context of the 95% confidence interval that surrounds it. It will also be interpreted within the context of other important information such as the clinical significance of study findings, and existing data from prior relevant studies.

During the innovation and usability phase, the VR device will record usage frequency and time as measures of adherence. Satisfaction and usability ratings will result from self-report when participants return the VR equipment as well as real-time measures concerning changes in PLP symptoms while using the VR headset, with the study goal of achieving a mean 80% satisfaction/usability rating on Likert scale items.

Regarding the feasibility trial Aims 2-3, we will assess feasibility of the study and if the use of the VR and mirror therapy treatments are associated with reductions in PLP, mood symptoms, or improvements in function. We will focus on our ability to implement recruitment strategies, conducting this innovative treatment and measurements, recruitment rate, consent rate, reasons for not participating, reasons for dropping off, the rate of missing data, pattern of missing values, adherence rate and subjects satisfaction. Data analyses will proceed in stages. At first, descriptive statistics and exploratory graphing such as frequencies, means, standard deviations, box and whisker plots, stem and leaf diagrams, and scatter plots will be used to assess the distribution and normality of the data in terms of the presence of skew and/or outliers. The continuous outcome data will be transformed if necessary by using an appropriate transformation such as the log transform for skewed long tailed data. Similarly, potential covariates will also be summarized with descriptive statistics and graphs to determine the most appropriate way to treat these variables to determine if a continuous, categorical, or an interval representation is the most appropriate approach. The comparability of the two treatment groups in baseline demographic and clinical features will be tested with analyses of variance (ANOVAs) for continuous variables and Chi-square analyses for dichotomous variables. Our randomization procedure is expected to control patient and treatment variables that might be associated with outcome. Any variables on which the groups differ initially will be explored as covariates in subsequent analyses, and we will take this into account in the interpretation of the outcome. Primary analyses will be based on a hierarchical model (HLM) using an intent-to-treat method that uses all available data. The model will include a random intercept, a random effect for assessment time, and fixed effects for comparison groups and group-by-time interaction. Denominator degrees of freedom will be calculated using the Kenward-Roger small sample correction. Data will be analyzed from all randomized subjects on whom we have a baseline assessment and at least one post-baseline evaluation. All hypothesis tests will be two-sided with alpha set at .05 and a medium to large effect size (i.e., Cohen's  $d \geq 1.0$ ) for changes from baseline to treatment. We will control Type I error by reducing measures to one key variable or a total or composite score when possible and will use Bonferroni correction for secondary outcomes in a domain family and secondary analyses. Using statistical power software for independent sample designs, an  $N$  of 10 for each treatment group and a minimum effect size of 1.0 standard deviation units of PLP (approximately two points on the PLPQ) results in an estimated power of .72 for the within group changes from pre- to post-treatment. The feasibility trial is not powered to detect between group differences. Based on our previous R&D trial, it will require several years of recruitment in a larger study to enable appropriately powered between group comparisons with a PLP sample. However, we will examine group means and standard deviations for the purpose of calculating effect sizes for a future trial application.

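### Baseline PLPQ adjustment is not prespecified for the between-arm comparison, so the effect size for the future trial loses precision and carries chance baseline imbalance at 10 per arm (minor; nearly free to fix)

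*Combined protocol and SAP*

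**What the plan says.** All of the analysis text is in Section C, Data Management and Statistical Analyses.

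- Baseline features of the two arms "will be tested with analyses of variance (ANOVAs) for continuous variables and Chi-square analyses for dichotomous variables". The section sets a two-sided alpha of .05 for all hypothesis tests.
- The covariate rule follows: "Any variables on which the groups differ initially will be explored as covariates in subsequent analyses". For those same variables, "we will take this into account in the interpretation of the outcome". No covariate is named in advance.
- The primary model has a random intercept, a random effect of time, and "fixed effects for comparison groups and group-by-time interaction". It lists neither a baseline PLPQ covariate nor a constraint that the arms share a baseline mean.
- The analysis set is randomized patients "on whom we have a baseline assessment and at least one post-baseline evaluation". With the group-by-time term and the stated use of all available data, this implies that the baseline score is one of the modelled outcomes.
- For the between-arm effect size, "we will examine group means and standard deviations for the purpose of calculating effect sizes for a future trial application". The text does not say whether these are post-treatment or change values.
- The plan is candid about its limits: "The feasibility trial is not powered to detect between group differences", and it says that effect sizes are not its main focus.

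Table 2 schedules the PLPQ at baseline, Weeks 2-3 and Week 4. The Section B overview nevertheless lists effect-size and comparative data for a larger trial among the goals.

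**The concern.** With 10 patients per arm, sizeable baseline differences in pain arise by chance. Baseline pain is usually the best available predictor of later pain, so its place in the between-arm analysis should be fixed beforehand. Here it depends on a significance test with little power to notice imbalance.

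If the test does not flag baseline PLPQ, the listed model subtracts the whole baseline difference. This generally over-corrects: through regression to the mean, the arm that starts with more pain appears to improve more. An unadjusted comparison of post-treatment means would err in the opposite direction.

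At stake is the quality of one number, the between-arm effect size carried into planning the larger trial. The within-arm results and the feasibility outcomes are not at stake.

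**Working it through.** The plan gives no figure for between-arm precision, so there is none to reproduce. Its power of .72 is for within-arm change and is not used here.

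**Inputs from the documents:** 10 per arm; two-sided alpha .05; the listed model terms; the PLPQ schedule.

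**Assumed, because the documents give no value:** pre-post correlation ρ = .3/.5/.7; normal scores with SD 1 at both times; .05 as the meaning of a baseline difference. For the hierarchical model, also: linear time, visits at weeks 0, 2, 3 and 4, intercept share of baseline variance .3/.5/.7, and a slope variance. Results are in SD units throughout.

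**1. Chance imbalance and the flag.** The SE of the baseline difference is √(2/10) = 0.447. The test flags an observed difference above t(.975, 18) × √(2/10) = 2.101 × 0.447 = 0.94 SD. P(|imbalance| > 0.5) = 2 × [1 − Φ(0.5/0.447)] = 26%. In simulation, 81% of those trials go unflagged, which is 0.26 × 0.81 = 21% of all trials.

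**2. Shift from a 0.5 SD imbalance with no true difference.** The change-type contrast moves by (1 − ρ) × 0.5, in favour of the arm with higher baseline pain. The post-treatment contrast moves by ρ × 0.5 against that arm.

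| ρ | Change-type | Post-treatment means |
|---|---|---|
| .3 | 0.35 | 0.15 |
| .5 | 0.25 | 0.25 |
| .7 | 0.15 | 0.35 |

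**3. Precision, never adjusting against always adjusting.** Variances of the between-arm contrast are:
- change: 0.2 × 2(1 − ρ) = 0.280/0.200/0.120;
- post-treatment: 0.2 at every ρ;
- baseline-adjusted: 0.2 × (1 − ρ²) × (1 + 1/16) = 0.193/0.159/0.108, where the last factor is the small-sample cost of estimating the slope.

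The corresponding SEs are 0.53/0.45/0.35, 0.45, and 0.44/0.40/0.33. Always adjusting cuts variance by 31/20/10% against change scores and by 3/20/46% against post-treatment means.

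**4. Precision against the plan's test-then-adjust rule (simulation).** The rule adjusts when the test flags and otherwise falls back on the unadjusted contrast. Always adjusting cuts variance by about 25/16/8% if the fallback is change scores and about 3/16/39% if it is post-treatment means.

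**5. The listed hierarchical model.** Generalized least squares, variance components known, Week 4 group-by-time contrast, intercept-slope correlation 0. A 0.5 SD imbalance shifts the contrast by 0.36/0.26/0.15 SD with a free baseline and by 0 with a common baseline. The variance cut from a common baseline depends on the slope variance:

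| Slope variance per week² | Intercept share .3 | .5 | .7 |
|---|---|---|---|
| 0 | 46% | 32% | 18% |
| .02 | 37% | 23% | 12% |
| .08 | 23% | 13% | 6% |

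At slope variance .02 and intercept-slope correlation +.5, the cut falls to 23/9/1%; at −.5 it rises to 54/45/36%. With components estimated from 20 patients (500 simulated trials per cell, slope variance .02), it is about 36/16/8% at correlation 0 and can be nil at +.5.

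**The case against.** The strongest reply is that the plan already plays this number down. It disclaims between-arm power, puts feasibility first, and warns of the large standard error around a pilot effect size. The model uses baseline as an outcome, so it is not wholly unadjusted. The shifts in step 2 are below the SE of the contrast they affect. All of this stands, and it is why the point is minor.

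Several stronger readings are tempting, but the documents do not support them:

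- *That the comparison is biased or the test invalid.* Over randomizations neither contrast is biased and type I error is not inflated. The error is conditional on the imbalance that happens to occur.
- *That no cut-off exists for a baseline difference.* The section's .05 for all hypothesis tests supplies a natural one.
- *That unflagged imbalances are left to interpretation.* The clause "we will take this into account in the interpretation of the outcome" refers to variables on which the arms do differ, and it comes in addition to exploring them as covariates.
- *That flagged covariates may never reach the primary model.* The reference to subsequent analyses comes shortly before the primary model is described and naturally includes it.
- *That the promised interval is affected.* Section C says "we will calculate an estimated effect size for our primary outcome in the context of the 95% confidence interval that surrounds it", but not that this effect size is between arms. It may be the within-arm change, which this point leaves untouched.
- *That the choice of route moves the result by half an SD.* The two shifts in step 2 do add to 0.5 SD at any ρ. But the plan speaks mainly of change from baseline. Raw post-treatment means are permitted by silence, not proposed.

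**Conclusion.** The point holds as a minor, nearly free improvement. Baseline PLPQ adjustment of the between-arm contrast is not prespecified. It depends on a test that misses about four in five chance imbalances above 0.5 SD, and the fallback generally acts like a change score.

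On the change reading, adjustment always applied saves about 25/16/8% of between-arm variance at ρ = .3/.5/.7. On the post-treatment reading it saves about 3/16/39%. For the hierarchical model the saving runs from 46% to 6% over the slope variances tried at intercept-slope correlation 0, and it can be close to nil when that correlation is positive.

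These sizes rest on the assumed correlations, variance components, normality and .05 flag. That adjustment is not prespecified does not depend on them. Within-arm conclusions are unaffected. No conversion to PLPQ points is made, because the plan's two-point figure is given for within-arm change.

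**What to change.** 1. Describe baseline by arm without significance tests, and delete the rule that selects covariates from observed differences.
2. Prespecify baseline PLPQ adjustment for the between-arm analysis in one of two forms: a common baseline mean in the hierarchical model (time coded 0 at baseline, no group main effect), or post-baseline visits as outcomes with baseline PLPQ as a covariate.
3. Take the between-arm difference and its 95% CI for the future trial from that model, in PLPQ points.
4. Beside it, report baseline and post-treatment means and SDs by arm and the pre-post correlation. State which SD is used for any standardised effect. Do not rely on the baseline SD alone: the entry criterion of PLP at least 4/10 may narrow it and so enlarge the effect size.
5. Keep the within-arm pre-post analysis as planned.

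The cost is SAP wording. The PLPQ is already collected at baseline. The covariate form uses one degree of freedom, and the common-baseline form has one fixed effect fewer than the listed model.

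### The stated power of .72 for within-group change comes from an independent-samples calculation and does not reproduce at two-sided .05 (.56 by t, .61 by normal approximation)

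*Combined protocol and SAP*

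**What the plan says.** All the relevant statements about power are in section C, Data Management and Statistical Analyses.

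- Testing rule: "All hypothesis tests will be two-sided with alpha set at .05".
- Method of the power calculation: "Using statistical power software for independent sample designs".
- Inputs: an N "of 10 for each treatment group and a minimum effect size of 1.0 standard deviation units of PLP", described as roughly two PLPQ points.
- Result: this "results in an estimated power of .72 for the within group changes from pre- to post-treatment".
- Primary analysis: a hierarchical model with group and group-by-time fixed effects. "The model will include a random intercept, a random effect for assessment time".
- Analysis set: "Data will be analyzed from all randomized subjects on whom we have a baseline assessment and at least one post-baseline evaluation".

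The plan then says that the trial is not powered for between-group differences. It gives no pre-post correlation, no SD of change, and no statement that the power calculation was one-sided. The Recruitment Feasibility section projects dropout of about 10%, but the power sentence uses the full 10 per group.

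**The concern.** The power sentence has two separate faults.

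1. **The design does not match the claim.** An independent-samples calculation compares two different sets of people, whereas the claim concerns change within one set. For that change, the variance depends on how strongly a person's baseline and post-treatment scores are correlated. The plan supplies no such input. It also leaves open whether the 1.0 SD is the SD of scores or of change. The wording (SD units of PLP) points more naturally to scores, but the same paragraph also attaches an effect size of 1.0 to changes from baseline.

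2. **The number does not follow from the inputs** under the two-sided rule in the same paragraph.

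This is the only power figure in the plan. The plan does intend to examine whether each treatment is associated with a reduction in PLP, so a reader weighing a null within-arm result would rely on .72. Someone planning the larger trial might carry it forward.

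**Working it through.** **Inputs from section C:** n = 10 per group; effect d = 1.0; alpha = .05, two-sided; stated power .72.

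**Step 1. The calculation as described (independent samples).** The noncentrality is d × √(n/2) = 1.0 × √5 = 2.236, with 2n − 2 = 18 df.

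| Method | Two-sided .05 | One-sided .05 |
|---|---|---|
| Noncentral t, 18 df | .562 | .694 |
| Normal approximation | Φ(2.236 − 1.960) = .609 | Φ(2.236 − 1.645) = .723 |

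Only the one-sided normal approximation returns .72. It is a plausible source, but the plan does not confirm it. A two-sided independent t-test reaches .72 at 14 per group (.721; 13 per group gives .687), or with 10 per group at d of about 1.20.

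**Step 2. The contrast that the sentence claims (within-arm change).** If 1.0 is the SD of scores, equal at both times, the SD of change is √(2(1 − r)) in score-SD units. The standardised change is then dz = 1/√(2(1 − r)), with noncentrality dz × √n. The plan gives no r, so the values below are assumptions. The pooled column takes the variance of change over both arms and is only a rough stand-in for the planned model.

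n = 10 per arm, two-sided .05:

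| Assumed r | dz | Noncentrality | Paired t (9 df) | Pooled variance (18 df) |
|---|---|---|---|---|
| 0 | 0.707 | 2.236 | .51 | .56 |
| .3 | 0.845 | 2.673 | .66 | .72 |
| .5 | 1.000 | 3.162 | .80 | .85 |
| .7 | 1.291 | 4.082 | .95 | .97 |

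The r = 0 row has the same noncentrality as step 1, and its pooled result equals the two-sided independent t result. Using independent-samples software therefore amounts to assuming no correlation between a person's two scores.

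Power equals .72 at r = .39 (paired t) or r = .31 (pooled). Below those values .72 is too high; above them it is too low.

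**Step 3. If 1.0 is the SD of change.** Then dz = 1.0 and the noncentrality is √10 = 3.162. Power is .80 (9 df) or .85 (18 df).

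**Step 4. Attrition.** About 10% dropout leaves 9 of 10 per arm if those who drop out give no post-baseline value. On the change-SD reading, power is then .75 (paired t, 8 df) or .80 (pooled, 16 df). On the score-SD reading, paired t gives .46, .60, .75 and .92 at r = 0, .3, .5 and .7.

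**The case against.** The strongest reply is that .56 and .61 are the power of a between-group comparison, which the plan disclaims. They are therefore not the power of the within-group contrast and do not show that .72 is overstated. That is correct. The two-sided within-arm range in step 2 contains .72, and on the change-SD reading .72 is conservative. The figures in step 1 show only that the stated number does not follow from the stated method and testing rule.

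It can also be said that the two-sided rule is written for hypothesis tests and that the sidedness of the power calculation is not stated. That too is fair. But a one-sided power figure for tests that will be two-sided would still describe a different test from the one planned.

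A third reply is that paired t-tests ignore the PLPQ assessments at weeks 2–3 that the hierarchical model will use. This stands as a limit on the figures in steps 2 to 4, and it is a reason to allow a model-based calculation as the repair. It does not support .72, which was not obtained from that model.

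Finally, this is a feasibility study. The plan says that "although we will estimate effect sizes to assist in future power calculations, this is not our major focus", and it sets no sample size, stopping rule or go/no-go criterion from .72. That limits the consequence but does not make the figure right.

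**Conclusion.** The concern holds. The plan reports the output of an independent-samples calculation as power for a within-person change. At two-sided .05 its inputs give .56 (t) or .61 (normal approximation), which is 16 or 11 percentage points below .72. This part rests only on figures in section C.

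The direction of the error in within-arm power cannot be settled from the documents. With 10 per arm and assumed correlations from 0 to .7, power runs from .51 to .97 over the paired and pooled calculations on the score-SD reading. It is .80 to .85 on the change-SD reading. The correlations and the pooled approximation are assumptions. This should be corrected, but it is a reporting error and does not threaten the design.

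**What to change.** Replace the power sentence with a two-sided calculation for within-arm change, either paired or from the planned hierarchical model, and remove the reference to independent-sample designs. State:

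1. whether 1.0 SD (about two points) is the SD of PLPQ scores or of change;
2. the assumed pre-post correlation and its source;
3. the number per arm expected to contribute a post-baseline value, consistent with the projected dropout.

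If no correlation can be sourced, report a range rather than one number. For example: *With 10 per arm, two-sided alpha .05 and a change of 1.0 SD of scores, a paired t-test has power .51, .66, .80 and .95 for pre-post correlations of 0, .3, .5 and .7.* If 9 per arm are expected to contribute, the corresponding values are .46, .60, .75 and .92.

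The cost is a rewrite of one paragraph, with no added patients, visits or analyses.
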